## 1. **BACKGROUND**

### 1.1 **BACKGROUND ON SPINAL MUSCULAR ATROPHY (SMA)**

Spinal muscular atrophy (SMA) is an autosomal recessive neuromuscular disorder clinically characterized by progressive muscular weakness and atrophy. SMA is the most common genetic cause of infant mortality with an estimated incidence of 1 in 6,000 to 10,000 live births ([Prior 2010](#)). In most patients, the disease results from homozygous deletion or mutation of the survival motor neuron protein (SMN) gene SMN1 ([Lefebvre et al. 1995](#)). In humans, there are two SMN genes, the telomeric SMN1 gene and the centromeric SMN2 gene, resulting from intra-chromosomal duplication of 5q13. The only critical difference is an 840 C-to-T mutation in the SMN2 gene that excludes exon 7 from approximately 85-90% of transcripts, resulting in an unstable protein ([Markowitz et al. 2012](#)). Clinical severity is inversely correlated with SMN2 gene copy number ([Kolb and Kissel 2011](#)).

SMA leads to predominantly proximal muscle atrophy and weakness and the potential for medical complications such as scoliosis, joint contractures and restrictive lung disease due to respiratory muscle weakness. Progressive respiratory failure and frequent pulmonary infections are common in SMA Type 1 and 2, so that in severe phenotypes non-invasive respiratory support is often needed. Other common comorbidities include failure to thrive, sleep difficulties, pneumonia, osteopenia and osteoporosis with pathological fractures, poor cough and secretion clearance, reduced vital capacity, gastro esophageal motility disorder, urinary incontinence, hip dislocation, and joint and muscle pain.

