4.3.1 Demographics

Summary statistics will be presented for the following demographic and baseline characteristics: age (at the time of first treatment in the open-label part of the study), sex, race, ethnicity, country, weight, height, body mass index (BMI) and tanner stage (for patients 9-17 years old).

If height cannot be measured directly (e.g. due to scoliosis or contractures) ulnar length will be used to calculate a surrogate height measure. For patients with an ulnar length measurement available and height indicated as 'derived' in the electronic case report form (eCRF), height will be derived from the measurement of ulnar length using the following formulae:

For patients 5-19 years old (Gauld et al. 2004):

$$\text{Female: height (cm)} = 4.459 * \text{ulnar length (cm)} + 1.315 * \text{age (years)} + 31.485$$

$$\text{Male: height (cm)} = 4.605 * \text{ulnar length (cm)} + 1.308 * \text{age (years)} + 28.003$$

For patients > 19 years old (Elia 2003):

$$\text{Female: height (cm)} = 95.6 + 2.77 * \text{ulnar length (cm)}$$

$$\text{Male: height (cm)} = 79.2 + 3.60 * \text{ulnar length (cm)}$$

Percentiles for weight-for-age, stature-for-age, weight-for-stature and BMI-for-age will also be presented for all patients. These will be based on the Centers for Disease Control and Prevention (CDC) growth standards. For patients > 20 years (240 months) old, percentiles will be based on the reference data for individuals 240 months of age. Percentiles for stature-for-age, weight-for-stature and BMI-for-age may be presented separately for patients whose height can be measured directly and those whose height cannot be measured directly.

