4.4 EFFICACY ANALYSIS

As this is a single arm, open-label study no formal hypothesis testing will be performed. Data collected during the treatment phase of this study will be summarized using descriptive statistics and will be compared with observational data describing the natural history of the disease.

The baseline value will be defined as the last non-missing value recorded prior to or on the first day of the study drug (Study Day 1).

Post-baseline efficacy assessments (scheduled every 26 weeks), including assessments performed at an early discontinuation visit, will be assigned to a scheduled study visit based on the following time windows:

Visit	Study Day	Time Window (in Study Days)
V3 (Week 26)	183	Day 2 – Day 274
V5 (Week 52)	365	Day 275 – Day 456
V6 (Week 78)	547	Day 457 – Day 638
V7 (Week 104)	729	Day 639 – Day 820
V8 (Week 130)	911	Day 821 – Day 1002
V9 (Week 156)	1093	Day 1003 – Day 1184
V10 (Week 182)	1275	Day 1185 – Day 1366
V11 (Week 208)	1457	Day 1367 – Day 1548
...		

If multiple valid values for a variable are recorded in the same time window, the record closest to the scheduled study visit will be selected for summary of the data.

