4.6.5 Vital Signs

Vital signs assessments, including temperature, respiratory rate, pulse rate, blood pressure, weight, height and BMI will be measured throughout the study. If height cannot be measured directly, ulnar length will be used to calculate a surrogate height measure as described in Section 4.3.1. Summaries for vital signs will be presented at each time-point for actual values and change from baseline values. Percentiles for

weight-for-age, stature-for-age, weight-for-stature and BMI-for-age and change from baseline percentiles will also be presented for all patients.

Vital signs data will be listed for patients with values outside the normal ranges for temperature, respiratory rate, pulse rate, systolic blood pressure and diastolic blood pressure. The normal ranges will be based on the age of the patient at the time of the assessment. In addition, shift tables to compare the status at baseline to each time-point post-baseline and overall will be presented. The following normal ranges will be used:

Age (months)	Heart/Pulse Rate (beats/min)	Respiratory Rate (breaths/min)	Systolic Blood Pressure (mmHg)	Diastolic Blood Pressure (mmHg)	Temperature (°C)
>24 and ≤144		18-30	80-125	40-80	35.5-37.8
>144	50-100	12-20	90-140	40-120	36.5-37.5
>72 and ≤96	60-110				
>96 and ≤144	55-100				

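### The only age-adjusted growth measure in the SAP is change in CDC percentile, which is compressed for patients who start low; change in z-score should be shown beside it

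*SAP*

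**What the plan says.** SAP 4.6.5 treats body size as part of vital signs: "Vital signs assessments, including temperature, respiratory rate, pulse rate, blood pressure, weight, height and BMI will be measured throughout the study". Two kinds of growth summary follow.

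- Raw units: "Summaries for vital signs will be presented at each time-point for actual values and change from baseline values". This covers weight, height and BMI.
- Percentiles, as an addition: "weight-for-age, stature-for-age, weight-for-stature and BMI-for-age and change from baseline percentiles will also be presented for all patients".

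SAP 4.3.1 gives the reference for the percentiles: "These will be based on the Centers for Disease Control and Prevention (CDC) growth standards". For patients older than 20 years the reference age is frozen: "percentiles will be based on the reference data for individuals 240 months of age".

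Neither document plans a z-score (SD score) for growth. The out-of-range listing does not fill the gap: "Vital signs data will be listed for patients with values outside the normal ranges for temperature, respiratory rate, pulse rate". It goes on to systolic and diastolic blood pressure, and the normal-range table has no column for weight, height or BMI.

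Protocol 1.1 describes the disease background: "Other common comorbidities include failure to thrive, sleep difficulties, pneumonia, osteopenia and osteoporosis with pathological fractures".

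**The concern.** A percentile is bounded at 0 and 100 and strongly non-linear near the ends, so the same loss in SD units gives very different percentile changes depending on where the patient starts. If part of the cohort starts well below the reference median, as the comorbidity list makes plausible, their changes contribute little to a mean percentile change, whatever happens to them.

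The raw summaries have the opposite limitation. They are linear, but normal growth raises them. A growing child who gains less than expected still shows a positive change in kg or cm, and the mean mixes such children with older patients.

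Safety is the primary objective (Protocol 2.1), vital signs are among the parameters it names, and treatment may continue for up to four years after the last enrolment (Protocol 3.2). At stake is whether a reader of the vital-sign tables could recognise slow growth in patients who were already small at baseline.

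**Working it through.** The documents state no figure on this point, so there is nothing of the plan's own to reproduce. The check covers the scale itself.

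**Inputs.** The percentile measures and reference come from SAP 4.6.5 and 4.3.1. Two things are assumed: a growth percentile is the normal probability of its z-score, and a range of starting points is needed because no baseline growth distribution is given.

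**Formula.** Percentile = 100 × Φ(z). For a loss of d SD from a start at z0, percentile change = 100 × [Φ(z0 − d) − Φ(z0)].

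| Start z0 | Start percentile | Change, 0.5 SD loss | Change, 1 SD loss | 1 SD loss relative to median start |
|---|---|---|---|---|
| 0 | 50.0 | -19.1 | -34.1 | 100% |
| -1 | 15.9 | -9.2 | -13.6 | 40% |
| -1.645 | 5.0 | -3.4 | -4.6 | 13% |
| -2 | 2.28 | -1.7 | -2.1 | 6% |
| -2.5 | 0.62 | -0.49 | -0.60 | 1.8% |
| -3 | 0.13 | -0.11 | -0.13 | 0.4% |

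On the z-score scale, a 1 SD loss reads -1.00 in every row.

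**Effect on a mean.** Suppose 25% of patients start at z = -2.5 and lose 1 SD, and the rest stay at the median. The mean percentile change is 0.25 × (-0.598) = -0.15 points. If the 25% who lost 1 SD had started at the median, it would be 0.25 × (-34.1) = -8.5 points. The mean z-score change is -0.25 in both cases. For single patients, a fall of 0.1 SD from the median (-4.0 points) counts more than a fall of 1 SD from z = -2.5 (-0.60 points).

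**What the raw table adds.** As an illustration, assume a reference median rising from 20 to 23 kg and a coefficient of variation of 15%, so weight = median × (1 + 0.15 z). A child at z = -2 starts at 20 × 0.70 = 14.0 kg.

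- Holds z = -2: 23 × 0.70 = 16.1 kg, a gain of 2.1 kg.
- Falls to z = -2.5: 23 × 0.625 = 14.4 kg, a gain of about 0.4 kg, with a percentile change of -1.7.
- Falls to z = -3: 23 × 0.55 = 12.65 kg, a loss of 1.35 kg, with a percentile change of -2.1.

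The raw table shows the 1 SD fall as a loss. It shows the 0.5 SD fall as a small gain, with no benchmark of 2.1 kg beside it.

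Under the same assumed variation, a 0.5 SD fall from z = -2 appears as a raw gain once the reference median has risen by more than 0.70/0.625 = 1.12, that is 12%. A 1 SD fall does so after a rise of 0.70/0.55 = 1.27, that is 27%. The safety windows in SAP 4.6 run to Week 208 and beyond, so how much the reference median rises depends on age and follow-up.

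**The case against.** A reader might infer that growth is reported only as percentile change, so that loss of growth would be hidden. The documents do not support that. SAP 4.6.5 adds the percentiles to summaries of actual values and change in raw units, and in the illustration a fall from z = -2 to z = -3 appears there as a loss of 1.35 kg. That objection stands, and it limits the point to insufficient gain rather than outright loss.

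A reader might also infer that many patients sit in the lowest percentiles. Protocol 1.1 is a background list for SMA in general and gives no frequency. The cohort is essentially Type 2 and non-ambulatory Type 3, and Protocol 1.2.2 links worsening at 6–15 years to growth and weight gain without added strength. The share in the low tail is simply unknown. Nor does compression make the change negligible for every small child: from the 5th percentile, a 1 SD loss still reads -4.6 points.

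Many patients may have stopped growing. The placebo-controlled trial enrolled ages 3–25 for 24 months, and Protocol 1.2.2 gives 2.4–4.0 years since last dose. That puts baseline ages at roughly 3 + 2 + 2.4 = 7 to 25 + 2 + 4 = 31 years. For those past growth, raw change is not inflated by normal growth and the gap largely disappears. It remains for the younger patients.

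There is other capture as well. Weight is measured at every scheduled treatment visit, and clinically significant new or worsened findings are to be recorded as adverse events (Protocol 4.4.5 and 5.3.5.8). This covers recognised cases, but it does not replace an age-adjusted summary.

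Finally, growth is not a named objective, and the analysis is descriptive. SAP 4.4 says of efficacy: "As this is a single arm, open-label study no formal hypothesis testing will be performed". No error rate or sample size is affected. That is a reason to rate the point low, not to drop it.

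**Conclusion.** The point holds in a narrow form. Percentile change is the only age-adjusted growth measure planned, and it is compressed in the low tail: a 1 SD loss shows 13% of its median-start size from the 5th percentile, 6% from z = -2 and 0.4% from z = -3. Raw change shows outright loss but does not adjust for expected growth. In growing patients who start low, too little gain therefore has no uncompressed age-adjusted summary.

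The scale figures rest only on the normal relation between percentile and z-score. The kg figures rest on an assumed reference median and variation. The practical effect depends on how many growing patients start low, which the documents do not give. The documents do not support a conclusion that faltering growth would go unseen in this study. This is a minor improvement to a descriptive safety display.

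**What to change.** In SAP 4.3.1, add baseline CDC z-scores for weight-for-age, stature-for-age and BMI-for-age, for patients up to 20 years. In SAP 4.6.5, add the z-score and its change from baseline at each time-point for the same patients. Keep the percentiles and raw summaries as they are.

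A count of patients with a large fall in z-score may be added as a descriptive display only. The documents give no basis for a particular cut-off, and measurement noise would enter the count. Height may be derived from ulna length with a formula that changes at age 19 (SAP 4.3.1). Weight is recorded to the nearest kilogram (Protocol 4.4.4); in the 20 kg illustration the SD is 0.15 × 20 = 3 kg, so rounding alone can move a reading by up to 0.5/3 = 0.17 SD.

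The cost is SAP wording and one more descriptive table. No new measurement, visit or reference data are needed.

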### **5.3.5.5 Abnormal Vital Sign Values**

Not every vital sign abnormality qualifies as an adverse event. A vital sign result must be reported as an adverse event if it meets any of the following criteria:

- Is accompanied by clinical symptoms
- Results in a change in study treatment (e.g., dosage modification, treatment interruption, or treatment discontinuation)
- Results in a medical intervention or a change in concomitant therapy
- Is clinically significant in the investigator's judgment

It is the investigator's responsibility to review all vital sign findings. Medical and scientific judgment should be exercised in deciding whether an isolated vital sign abnormality should be classified as an adverse event.

If a clinically significant vital sign abnormality is a sign of a disease or syndrome (e.g., high blood pressure), only the diagnosis (i.e., hypertension) should be recorded on the Adverse Event eCRF.

Observations of the same clinically significant vital sign abnormality from visit to visit should only be recorded once on the Adverse Event eCRF (see Section 5.3.5.3 for details on recording persistent adverse events).

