2. STUDY DESIGN

Study BN29854 is a phase II, multicenter, open-label, single arm study to evaluate the long-term safety, tolerability and effectiveness of olesoxime (Roche No. RO7090919) 10mg/kg q.d. in patients with SMA who previously participated in one of the following two studies:

- Open-label phase Ib, dose-ranged, single and multiple dose study to assess safety and pharmacokinetics of olesoxime in 6-25 year old SMA patients (Trophos No. TRO19622CLEQ1115-1, Roche No. WP29845), and
- Phase II multicenter, randomized, adaptive, double-blind, placebo controlled study to assess safety and efficacy of olesoxime in 3-25 year old Type 2 or non-ambulatory Type 3 SMA patients (Trophos No. TRO19622CLEQ1275-1, Roche No. WN29836).

The study will consist of historical data collection, screening, treatment and safety follow-up periods. Patient visits will occur at 13, 26, 39 and 52 weeks and every 26 weeks thereafter for medical examinations, as well as safety and efficacy assessments. In addition, patients and their treating physicians will be requested to provide data for the period between the patients' last visit in the previous Trophos study and the screening period of study BN29854. Enrollment in the open-label treatment phase of the study is independent from the historical data collection, and a separate Informed Consent Form is required for each part. Patients (or their legal representatives) who do not consent to the historical data collection are still eligible to participate in the treatment phase of the study, and vice versa. The analysis methods that will be used for the historical data will be reported in a separate statistical analysis plan (SAP).

The study will continue until olesoxime is commercially available in the patient's country, or as per local regulation, or per the Sponsor's decision to terminate the olesoxime program for SMA, but will not exceed four years after the last patient was enrolled in the study. In the UK the study will last for a fixed period of three years after the last patient was enrolled.

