4.6 SAFETY ANALYSES

All safety variables will be summarized using descriptive statistics. Analyses will be based on the safety population.

Post-baseline safety assessments, including assessments performed at an unscheduled visit or at an early discontinuation visit, will be assigned to a scheduled study visit based on the following time windows:

Visit	Study Day	Time Window (in Study Days)
V2 (Week 13)	92	Day 2 – Day 137
V3 (Week 26)	183	Day 138 – Day 228
V4 (Week 39)	274	Day 229 – Day 319
V5 (Week 52)	365	Day 320 – Day 456
V6 (Week 78)	547	Day 457 – Day 638
V7 (Week 104)	729	Day 639 – Day 820
V8 (Week 130)	911	Day 821 – Day 1002
V9 (Week 156)	1093	Day 1003 – Day 1184
V10 (Week 182)	1275	Day 1185 – Day 1366
V11 (Week 208)	1457	Day 1367 – Day 1548
...		

These time windows will be used for all parameters, including those that were not scheduled to be collected at that visit. If multiple valid values for a variable are recorded in the same time window, the record closest to the scheduled study visit will be selected for summary of the data.

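### The diastolic upper normal limit rises from 80 to 120 mmHg at 144 months, out of proportion to the systolic limit, so values of 81-120 mmHg above that age are neither listed nor counted as high

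*SAP*

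**What the plan says.** SAP 4.6.5 plans three range-related or descriptive outputs for vital signs.

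- A listing: "Vital signs data will be listed for patients with values outside the normal ranges". Diastolic pressure is one of the five signs that it covers.
- Shift tables: "shift tables to compare the status at baseline to each time-point post-baseline and overall will be presented".
- Summaries that do not use the ranges: "Summaries for vital signs will be presented at each time-point for actual values and change from baseline values".

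The range applied depends on age at each assessment: "The normal ranges will be based on the age of the patient at the time of the assessment". The table then gives diastolic 40-80 mmHg and systolic 80-125 mmHg for patients over 24 and up to 144 months, and diastolic 40-120 mmHg and systolic 90-140 mmHg for patients over 144 months. The row for over 144 months has five entries under five column headings, so 40-120 belongs to diastolic pressure and has not slipped from another column. The SAP gives no source for any of the vital sign ranges.

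**The concern.** The diastolic limit is out of step with the rest of the same table. It is the only parameter whose range becomes much wider at 144 months, and it does so while the systolic upper limit moves by a modest amount.

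Vital signs are part of the primary objective (Protocol 2.1). For ECG, SAP 4.6.6 adds tables of fixed thresholds and of increases from baseline. Section 4.6.5 has no counterpart, so the listing and the shift tables are the only outputs planned there that classify individual blood pressure values. If the upper limit is set far too high, a reader of those two outputs would see few or no high diastolic values in older patients and could take that as reassurance. For a patient who passes 144 months on study, the shift table could show high to normal when the pressure has not fallen.

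**Working it through.** **Inputs.** All limits come from the range table in SAP 4.6.5.

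**Step 1: change in each range at 144 months.**

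| Parameter | Up to 144 months | Over 144 months | Upper limit | Width |
|---|---|---|---|---|
| Diastolic (mmHg) | 40-80 | 40-120 | 120 - 80 = +40 (+50%) | 40 to 80 |
| Systolic (mmHg) | 80-125 | 90-140 | 140 - 125 = +15 (+12%) | 45 to 50 |
| Pulse (beats/min; younger row is over 96 to 144 months) | 55-100 | 50-100 | 0 | 45 to 50 |
| Respiratory rate (breaths/min) | 18-30 | 12-20 | 20 - 30 = -10 | 12 to 8 |
| Temperature (°C) | 35.5-37.8 | 36.5-37.5 | -0.3 | 2.3 to 1.0 |

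Only the diastolic range doubles.

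**Step 2: values that change status.** A value is high if it exceeds the upper limit. At 80 mmHg it is normal in both rows, and at 121 mmHg it is high in both. Every whole value from 81 to 120 is high in the younger row and normal in the older one: 120 - 81 + 1 = 40 values.

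**Step 3: the two pressures together.** The gap between the systolic and diastolic upper limits falls from 125 - 80 = 45 mmHg to 140 - 120 = 20 mmHg. In a patient over 144 months, 140/120 lies at the upper limit on both and is classed as normal.

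**Step 4: effect on a shift table.** Take a baseline before 144 months and an assessment after it. An unchanged 90 mmHg is tabulated as high to normal. So is a rise from 85 to 118 mmHg, although the change-from-baseline summary would carry it as 118 - 85 = +33 mmHg.

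**Step 5: how often the high flag could fire.** The documents give no diastolic distribution. As an illustration only, assume normal readings with mean 65-75 and SD 8-12 mmHg.

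- Share above 80: from 1 - Φ((80 - 65)/8) = 0.030 to 1 - Φ((80 - 75)/12) = 0.338, that is, 3% to 34%.
- Share above 120: at most 1 - Φ((120 - 75)/12) = 0.000088, fewer than 1 in 10,000.

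**Step 6: who is affected.** The age subgroups in SAP 4.4.5 are 6-15 and 16 or more years. The older group lies wholly above 144 months (12 years), and the younger group spans the cut. Treatment may last for years; SAP section 2 says that the study "will not exceed four years after the last patient was enrolled in the study". Crossing on study is therefore possible, but the documents do not say how many patients will do so.

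**The case against.** The strongest reply is that little depends on this cell. "All safety variables will be summarized using descriptive statistics" (SAP 4.6), and no stopping rule, estimate or analysis population rests on the listing. Actual values and changes from baseline are summarized without the ranges. Protocol 5.3.5.5 adds a route outside the listing: "A vital sign result must be reported as an adverse event if it meets any of the following criteria", and these cover symptoms, a change in study treatment, an intervention or change in concomitant therapy, and clinical significance in the investigator's judgment. All of this stands. It limits the damage to two outputs but does not make them right: means can hide individual outliers, and adverse event reporting relies on judgment at the site.

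A reader might infer that raised diastolic pressure in patients over 12 is not flagged at all. The plan does not support that, because values above 120 mmHg are still listed and counted as high.

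A reader might also infer that 120 is a proven mistake. The documents do not establish this. They give no source for the ranges, and other limits also widen at this age: in SAP 4.6.6 the upper QT limit goes from 390 to 500 ms. A deliberately broad range cannot be excluded. The internal mismatch justifies a check, not a replacement value.

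Finally, a reader might conclude that shift tables must use the same limits at baseline and afterwards. Ranges by age at assessment are a stated choice, and at the same cut they also change status for systolic pressure, respiratory rate and temperature. Fixing one set of limits would judge either an older patient by childhood limits or a childhood baseline by later ones. That is a trade-off, not an error in the plan.

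**Conclusion.** The point holds for the limit itself. Followed as written, SAP 4.6.5 leaves diastolic values of 81-120 mmHg in patients over 144 months out of the listing and out of the high category in the shift tables, and an unchanged value in that band turns from high to normal at the cut. This follows from the table alone and needs no outside blood pressure standard.

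How many of those values ought to be flagged depends on the intended limit, which the documents do not give. If it lay anywhere from 80 to 95 mmHg (an assumption to show the range, not a proposal), values up to 120 - 80 = 40 or up to 120 - 95 = 25 mmHg above it would be called normal, and the missed band would run from 81-120 down to 96-120 mmHg. That the high flag would almost never fire above 144 months rests on the assumed distribution in the check. The size of the crossing effect cannot be stated without the number of patients who pass 144 months on study.

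The importance is minor to moderate: two safety outputs can mislead, other safety information remains, and the remedy is cheap.

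**What to change.** Before the listings and shift tables are produced, check the diastolic upper limit for patients over 144 months against its source. Reconcile it with the row for 144 months and below and with the systolic column. Correct the cell if it is an error; if it is intended, cite the source and give the reason in SAP 4.6.5.

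Optionally, footnote in the shift tables the patients whose age band differs between baseline and the assessment, so that a change of status caused only by the change of range can be recognized. This keeps the age-at-assessment rule.

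The cost is one table cell or one sentence, plus the footnote if adopted. No new data or visits are needed. If the limit is lowered, more values from patients over 144 months will appear in the listing, and possibly more than a few.
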